### **3.7 Data Management and Statistical Analysis**

Statistical analyses will be performed using SPSS version 22.0. Categorical variables will be expressed as n (%) and compared using the Chi-square ( $\chi^2$ ) test. Continuous variables will be tested for normality using the Shapiro-Wilk test (S-W test). Data conforming to normal distribution will be presented as mean  $\pm$  standard deviation ( $\bar{x} \pm s$ ), and comparisons between groups will be performed using the t-test. A P-value  $< 0.05$  will be considered statistically significant.

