## **Primary Objective**

To evaluate the safety and feasibility of an anastomotic technique designed to reconstruct ileocecal valve function during laparoscopic right hemicolectomy.

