## **3. Study Design**

### **3.1 Overall Study Design**

This study is a retrospective cohort study. Clinical data will be collected and analyzed from patients who underwent laparoscopic radical right hemicolectomy for colon cancer in our department. Patients will be categorized into two groups based on the type of anastomosis: the conventional anastomosis group and the ileocecal valve reconstruction group.

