### **3.3 Sample Size**

This is a retrospective cohort study. Based on screening of the hospital's electronic medical records and application of the predefined inclusion and exclusion criteria, a total of 50 patients were included. Among them, 30 patients underwent conventional anastomosis and 20 patients underwent ileocecal valve reconstruction. All surgeries and follow-up were conducted in the Department of General Surgery, Second Affiliated Hospital of Army Medical University.

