#### **Surgical Safety and Feasibility:**

Successful completion of surgery without anastomotic leakage, anastomotic bleeding, or stenosis.

No severe perioperative complications.

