### **3.6 Study Endpoints**

**Primary Endpoint:**

Postoperative complications within 30 days, specifically anastomotic leakage, anastomotic bleeding, and anastomotic stenosis.

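### Section 3.7 names only a chi-square test at P<0.05 to compare the primary safety endpoint in 20 vs 30 patients, which says little about safety when events are few; an unadjusted risk difference with its interval should be the main result

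*Protocol*

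**What the plan says.** The primary objective is "To evaluate the safety and feasibility of an anastomotic technique designed to reconstruct ileocecal valve function during laparoscopic right hemicolectomy". The primary endpoint (section 3.6) is "Postoperative complications within 30 days, specifically anastomotic leakage, anastomotic bleeding, and anastomotic stenosis". Section 3.6 does not say whether the three complications are combined or analysed one by one.

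Section 3.1 states "This study is a retrospective cohort study", with groups formed by the anastomosis performed. Section 3.3 takes the sample from the available records: "30 patients underwent conventional anastomosis and 20 patients underwent ileocecal valve reconstruction". It gives no power or precision figure.

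Section 3.7 sets the comparison: "Categorical variables will be expressed as n (%) and compared using the Chi-square" test, and a P-value below 0.05 "will be considered statistically significant". It does not say which chi-square version is meant, has no rule for small counts, and names no effect measure or interval. Section 3.4 describes safety and feasibility as "Successful completion of surgery without anastomotic leakage, anastomotic bleeding, or stenosis", together with no severe perioperative complications. That is a description, with no comparison attached.

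**The concern.** The objective is safety, but the one comparison named is a test for a difference. In 50 patients with a complication that may be uncommon, such a test will usually be non-significant, and with no events it gives no result. Neither outcome tells the reader how large an excess of complications the data still allow. The favourable case for the new technique, no events in either group, would leave the primary endpoint with no planned comparison.

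A lesser matter is that the chi-square is named without its version. In some sparse tables, choosing the version after seeing the data would decide which side of 0.05 the result falls.

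**Working it through.** **Inputs.** From section 3.3: 20 RISE and 30 conventional patients, 50 in total (20 + 30 = 50 agrees). From section 3.7: chi-square, threshold 0.05, taken as two-sided. The protocol gives no event rates, so every rate below is an assumption. There is no sample-size calculation to reproduce. Probabilities come from enumerating all 21 × 31 = 651 possible tables with two independent binomials.

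**1. Expected counts.** With m events in total (m up to 25), the smallest expected count is m × 20/50 = 0.4m. At m = 12 it is 4.8; at m = 13 it is 5.2. So it is below 5 unless at least 13 of 50 patients (26%) have an event. Probability of 12 or fewer events, binomial with n = 50:

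| Assumed overall rate | 10% | 15% | 20% | 25% |
|---|---|---|---|---|
| P(m ≤ 12) | 99.9% | 97.0% | 81.4% | 51.1% |

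**2. No events.** The chi-square statistic divides by p(1 − p), where p is the pooled rate, so it is undefined at p = 0. P(no events) = (1 − rate)^50: 61% at 1%, 36% at 2%, 7.7% at 5%.

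**3. Dependence on version, 3/20 vs 0/30.** Pooled rate 3/50 = 0.06; variance 0.06 × 0.94 × (1/20 + 1/30) = 0.0047.
- Pearson: 0.15² / 0.0047 = 4.79, P = 0.029.
- Continuity-corrected: (0.15 − 0.0417)² / 0.0047 = 2.50, P = 0.114, where 0.0417 = ½(1/20 + 1/30).
- Fisher: C(20,3)/C(50,3) = 1140/19600 = 0.058.

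Of the 90 tables with 1 to 12 events, Pearson and corrected verdicts differ in 8, and Pearson and Fisher in 3. Weighted by probability over all tables:

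| Assumed conventional vs RISE | Pearson and corrected differ | Pearson and Fisher differ |
|---|---|---|
| 5% vs 5% | 1.5% | 1.4% |
| 5% vs 15% | 10.1% | 5.4% |

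**4. False-positive rate.** Pearson at common rates of 5, 10, 15, 20 and 25%: 1.8, 3.2, 3.9, 4.3 and 4.4%. It is not inflated.

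**5. Power against harm.** At 5% vs 15%: Pearson 21%, Fisher 15%. For Pearson to reach 80% against 5%, the RISE rate must be about 35%.

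**6. What the interval shows.** Newcombe 95% limits for d = RISE minus conventional, where l and u are each group's Wilson limits (subscript 1 for RISE):
- lower = d − √[(p₁ − l₁)² + (u₂ − p₂)²]
- upper = d + √[(u₁ − p₁)² + (p₂ − l₂)²]

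0/20 vs 0/30: the Wilson upper limits are 3.84/23.84 = 16.1% and 3.84/33.84 = 11.4%, so the interval is −11.4 to +16.1 points.

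1/20 vs 1/30: the Wilson limits are 0.9 to 23.6% and 0.6 to 16.7%; d = 1.7; upper = 1.7 + √(18.6² + 2.7²) = +20.5, lower = −12.3. The Pearson P is 0.77.

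Exact (Clopper-Pearson) upper limit for 0/20: 1 − 0.025^(1/20) = 16.8%.

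**7. Consistency of interval and test.** Newcombe and uncorrected Pearson give the same verdict at 0.05 in all 649 tables with 1 to 49 events. In the 90 sparse tables, Newcombe and Fisher disagree in three: 3/20 vs 0/30 (+0.03 to +36.0, P = 0.058), 0/20 vs 6/30 (−37.3 to −0.8, P = 0.069) and 7/20 vs 3/30 (+2.0 to +47.7, P = 0.067).

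**The case against.** The strongest reply is that an interval, a sparse-table rule and a sentence on reading P are details a protocol may leave to its analysis plan, which is not shown. This stands in part: their absence alone would not be a finding. But section 3.7 does fix a test and a threshold for every categorical variable, and an analysis plan consistent with it would inherit that choice. The point is about the stated method.

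Second, a reader might infer that the test cannot inform safety at all. That is too strong. Counts and percentages are planned for each group, section 3.4 adds a descriptive criterion, a reader could derive the interval from the counts, and the test could detect a very large excess.

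Third, a reader might infer that the protocol means to treat P>0.05 as proof of safety. It does not say so.

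Fourth, one could note that at equal true rates of 2, 5, 10 and 15%, 98, 91, 85 and 84% of such studies would have a non-significant or undefined Pearson P while the interval allows more than 10 points of excess (an illustrative threshold). This mostly measures the sample size: ignoring P altogether, the figures are 98.5, 92.7, 87.3 and 86.0%. With 50 available records, no change to section 3.7 narrows the interval. It only makes the width visible.

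Finally, requiring Fisher in sparse tables and then letting the interval prevail would create three conflicts and resolve each in Pearson's favour. That objection is right, and the fix below does not require Fisher.

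**Conclusion.** The point holds as a weakness in a stated method and should be fixed. The chi-square test at P<0.05 is the only stated between-group comparison for the primary safety endpoint, and at 20 vs 30 a non-significant or undefined result leaves excesses of about 16 to 20 points open with 0 to 2 events in total. The unstated version matters in up to 10.1% of studies at an assumed 5% vs 15%, and in about 1.5% at 5% vs 5%.

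The expected-count threshold and the intervals for given tables follow from the group sizes alone. The probabilities and power rest on assumed event rates. The documents do not support a charge of inflated false positives, and they do not show that a non-significant result will be reported as safe.

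**What to change.** In section 3.7:

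1. For each of leakage, bleeding and stenosis, and for any of the three, report the rate in each group and the unadjusted risk difference (RISE minus conventional) with a 95% Newcombe interval, plus the exact upper limit for the RISE rate. State which of these four is primary, and make this the main result.
2. Label the difference descriptive, because the groups are not randomised, and state that P>0.05 is not evidence of safety.
3. Name one test version in advance, with P secondary. Uncorrected Pearson agrees with the interval wherever it is defined; with no events, report the interval alone. If Fisher is preferred for sparse tables, note its lower power (15% vs 21% at 5% vs 15%) and its three disagreements with the interval.
4. Give no safe/unsafe verdict. An acceptable excess named now could not be assumed blind to the results: section 3.3 places surgery and follow-up in the same department, and section 4.3 says patients were discharged before the study began.

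The cost is a few sentences, a closed-form calculation and no new data. The downside is that the safety result will look less certain than a bare P-value suggests.

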## 2. Objectives

This is a retrospective study that systematically collects data from patients who have undergone laparoscopic radical right hemicolectomy for colon cancer in our department. Patients are categorized into two groups based on the type of anastomosis: the conventional anastomosis group and the ileocecal valve function reconstruction group. This study aims to investigate the impact of ileocecal valve (ICV) function reconstruction on postoperative complications and bowel function recovery in patients following right hemicolectomy.

The outcomes of interest include anastomotic leakage, anastomotic bleeding, anastomotic stenosis, wound infection, time to first flatus, time to first defecation, time to stool formation, incidence of postoperative diarrhea, and Bristol Stool Form Scale classification.

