## **Secondary Objective**

To evaluate the clinical efficacy of ileocecal valve function reconstruction in laparoscopic right hemicolectomy, focusing on postoperative recovery of bowel function and reduction in gastrointestinal complications.

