### **3.2 Study Setting and Population**

This is a single-center observational study. All clinical data are derived from patients who have previously undergone laparoscopic radical right hemicolectomy in the Department of General Surgery.

Patients will be grouped according to the type of anastomosis (exposure factor):

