### **3.2.1 Inclusion Criteria**

Participants must meet all of the following criteria:

1. Aged between 18 and 80 years;
2. American Society of Anesthesiologists (ASA) physical status score of  $\leq 3$ ;
3. First-time diagnosis of colon cancer located in the appendix, cecum, ascending colon, hepatic flexure, or the right one-third of the transverse colon, including patients requiring additional surgery based on post-endoscopic pathological findings;
4. No history of other gastrointestinal diseases (except for benign conditions such as intestinal polyps or gallstones);
5. Complete and accessible clinical data.

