**Secondary Endpoints:**

Time to first flatus  
Time to first bowel movement  
Time to formed stool

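### Section 3.7 compares non-randomised groups with unadjusted tests, so an imbalance in factors prognostic for bowel recovery cannot be told apart from an effect of the anastomosis

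*Protocol*

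**What the plan says.** - **Design.** Section 3.1 states "This study is a retrospective cohort study". Sections 3.1 and 3.2 form the groups by the anastomosis each patient received and treat it as the exposure. No section says how the technique was chosen for a patient.
- **Group sizes.** Section 3.3: "30 patients underwent conventional anastomosis and 20 patients underwent ileocecal valve reconstruction".
- **Question.** Section 2 aims to "investigate the impact of ileocecal valve (ICV) function reconstruction on postoperative complications and bowel function recovery". The Secondary Objective is to "evaluate the clinical efficacy of ileocecal valve function reconstruction in laparoscopic right hemicolectomy, focusing on postoperative recovery of bowel function".
- **Endpoints.** Section 3.6 makes 30-day anastomotic leakage, bleeding and stenosis primary. The secondary endpoints are three recovery times: first flatus, first bowel movement, and "Time to formed stool".
- **Analysis.** Section 3.7 prescribes chi-square for categorical variables. For continuous variables that pass a Shapiro-Wilk check, "comparisons between groups will be performed using the t-test". The threshold is P < 0.05. No covariate, matching or stratification is named there or elsewhere.
- **Eligibility.** Section 3.2.1 admits ages 18 to 80, ASA class up to 3, and "First-time diagnosis of colon cancer located in the appendix, cecum, ascending colon, hepatic flexure, or the right one-third of the transverse colon".

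**The concern.** Nothing in the design makes the two groups comparable. Age, ASA class and tumour site are free to differ between them, and so are factors the protocol does not record. An imbalance matters only if the factor is also prognostic for the outcome. Where it is, the t-test in section 3.7 estimates the sum of the technique's effect and the case-mix difference, and the two cannot be separated afterwards.

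The objectives ask for the technique's effect alone. The stake is that a significant crude difference in recovery times is reported as efficacy of a new operation when case mix could account for it, or that case mix hides a real effect.

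**Working it through.** **1. The plan's own figures.** 30 + 20 = 50, which agrees with section 3.3. The protocol gives no power calculation, effect size, SD or event rate, so there is nothing further to reproduce. All bias sizes and risks below are assumptions. Sidedness is not stated; two-sided 5% is assumed.

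**2. Recovery times, crude t-test.** These figures apply to normally distributed times.

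SE of the standardised difference = √(1/30 + 1/20) = 0.289, with df = 48 and critical value c = 2.011. The 95% half-width is 2.011 × 0.289 = 0.58 SD.

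With no true effect and a net bias of b SD, the noncentrality is δ = b / 0.289, and the rejection rate is 1 − F(c; 48, δ) + F(−c; 48, δ), where F is the noncentral t distribution function.

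| Net bias b (SD) | δ | Rejection rate |
|---|---|---|
| 0.05 | 0.17 | 5.3% |
| 0.10 | 0.35 | 6.3% |
| 0.15 | 0.52 | 8.0% |
| 0.20 | 0.69 | 10.4% |
| 0.35 | 1.21 | 22.1% |

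Bias is imbalance times prognostic effect. For example, a binary factor worth 1 SD that is present in 60% of one group and 40% of the other gives (0.60 − 0.40) × 1 = 0.20 SD.

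**3. What adjustment does.** Simulation, 10,000 runs, 30 vs 20, no true effect, linear regression on group, age, ASA class and site (residual df 50 − 5 = 45). Age differences are in SDs of age; the slope is in outcome SDs per SD of age.

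| Scenario | Crude | Adjusted |
|---|---|---|
| Age 0.25 SD apart, slope 0.4 (bias 0.10) | 6.4% | 5.1% |
| Age 0.5 SD apart, slope 0.4 (bias 0.20) | 10.1% | 4.9% |
| As the row above, plus 0.20 SD unmeasured bias in the same direction | 27.3% | 10.9% |

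In the first two rows the return to about 5% holds by construction, because the simulated confounder is one of the adjusted variables. The third row shows the limit: the unmeasured 0.20 SD stays.

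Effect on precision:
- In the second row the mean SE goes from 0.287 to 0.280.
- In an unfavourable case (age 0.7 SD apart, ASA 3 in 40% vs 20%, site 60% vs 40%, none related to outcome) it goes from 0.288 to 0.327, which is 14% wider.

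**4. Primary endpoint, uncorrected chi-square.** Exact enumeration over both binomials. Any risk difference here comes from case mix alone. Half-width = 1.96 × √[p₁(1 − p₁)/30 + p₂(1 − p₂)/20]; expected events = 30p₁ + 20p₂.

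| Conventional vs reconstruction | Rejection rate | Half-width (points) | Events |
|---|---|---|---|
| 10% vs 10% | about 3% | 17.0 | 5.0 |
| 10% vs 7% | 2.7% | 15.5 | 4.4 |
| 7% vs 10% | 5.3% | 16.0 | 4.1 |
| 5% vs 10% | 8.8% | 15.3 | 3.5 |
| 10% vs 5% | 3.1% | 14.4 | 4.0 |

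A 3-point case-mix bias is about one fifth of the half-width (3 / 15.5 = 0.19). With about four events, a covariate model is not workable.

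**The case against.** The strongest reply concerns weight.

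- **Secondary endpoints only.** The primary objective is safety and feasibility. For the primary endpoint imprecision outweighs confounding, and the remedy leaves that comparison unadjusted. This is true and limits the point to the recovery times.
- **No harm is demonstrated.** The protocol gives no imbalance or prognostic strength. Halving the age slope to 0.2 makes the bias 0.5 × 0.2 = 0.10 SD and crude rejection 6.4%, which is slight. This stands; the figures are illustrations. The t-test figures also apply only to normally distributed times, since section 3.7 gives the t-test to those alone.
- **Restriction already controls some confounding.** Sections 3.2.1 and 3.2.2 cap ASA class and exclude other malignancy, infectious or autoimmune disease, and most other gastrointestinal disease. This narrows the cohort but does not balance the groups within it.
- **The covariates may not be the important ones.** The protocol does not say that age, ASA class or site predicts bowel recovery. Because section 3.2 describes the technique as novel, calendar period and surgeon experience are plausible confounders that the regression leaves untouched. This stands as a limit on what the remedy achieves, and it is why conclusions should be worded as associations even after adjustment.
- **A SAP might add adjusted analyses.** This carries little weight, because section 3.7 itself fixes the between-group tests.

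**Conclusion.** The concern holds. Section 3.7 names unadjusted tests for groups formed by the treatment received, and those tests cannot answer the question that the objectives pose. The claim is conditional: the protocol does not show that an imbalance exists, nor its size or direction.

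On assumed values, a net bias of 0.10 SD or less in a normally distributed recovery time does little harm (at most 6.3% against 5%). At about 0.20 SD the false-positive rate doubles (10.4%), and at 0.35 SD it exceeds four times nominal (22.1%). For the complication endpoint the main problem is imprecision, with half-widths of roughly 14 to 17 points on the assumed risks. The point should be fixed; it does not invalidate the study as a description of two series of patients.

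**What to change.** In section 3.7:

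1. Make the main analysis of each of the three recovery times a linear regression on group (on log time if skewed), adjusted for age, ASA class (3 vs 1-2) and tumour site in collapsed categories. Two site categories leave 45 residual df. Write down the site grouping and the rule for the log scale before outcomes are compared by group. Keep the crude tests as supportive.
2. Report baseline standardised differences and surgery dates by group.
3. Present the primary complication comparison as an unadjusted risk difference with a confidence interval, labelled descriptive.
4. Word all conclusions as associations, here and in the objectives.

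**Cost.** Protocol wording and a small amount of extra analysis. Age, ASA class and tumour site must already be extracted to apply section 3.2.1. Intervals for the recovery times may widen (14% in the unfavourable simulated case), unmeasured confounding remains, and the conclusions become more modest.

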## **4. Study-Related Costs**

## **4.1 Budget**

This is a retrospective cohort study. Data collection and analysis do not require dedicated funding.

## **4.2 Funding Source**

None.

## **4.3 Financial Burden to Participants**

All patients included in this study have completed surgery and were discharged prior to study initiation. This study involves retrospective data analysis only and will impose no additional financial burden on participants.

## **5. Quality Control**

This study will be led by a senior chief physician with extensive clinical and research experience. All other team members have completed Good Clinical Practice (GCP) training and will be responsible for patient observation, data recording, and data management. The overall quality of the study will be strictly controlled and ensured throughout the research process.

## **6. Ethical Principles and Requirements**

This clinical study will adhere to the ethical principles outlined in the Declaration of Helsinki (World Medical Association) and comply with the "Administrative Measures for Ethical Review of Life Science and Medical Research Involving Humans" issued by the People's Republic of China.

### **Key ethical considerations include:**

#### **Informed Consent:**

Before the study begins, the study protocol will be reviewed and approved by the Ethics Committee. If this study is not granted exemption from informed consent, the investigator has the responsibility to fully inform each participant and/or their legal representative about the study's purpose, procedures, and potential risks before enrollment.

Written informed consent will be obtained from all participants. Participation is entirely voluntary, and subjects may refuse to participate or withdraw from the study at any time without discrimination, penalty, or impact on their standard medical care or legal rights.

#### **Privacy and Confidentiality Protection:**

Investigators will take strict measures to protect the privacy and confidentiality of participants' personal information. All study data will be stored securely at the Second Affiliated Hospital of Army Medical University.

Exceptions to privacy protection will apply only in circumstances required by law or regulation, allowing study-related personnel, regulatory authorities, or ethics committees to review individual participant data when necessary for study oversight.

#### **Risk Control and Compensation for Research-Related Harm:**

The research team commits to minimizing risk and will provide appropriate protection for vulnerable populations if involved. Any research-related injury will be addressed according to applicable laws and regulations.

